**Table 4 Interim and Final Deliveries**

Analysis	Timing	Deliverable	Unblinded Team	Main Objective
Interim 1	90 subjects complete Week 4	PAREXEL: ADAM datasets and demography table (see Table 5 )  GSK: efficacy displays (see Table 5 ) and PK if required	Unblinded PAREXEL programmers, GSK lead and QC statistician, DRC	Evaluate whether to stop the study based on: • Dose response relationship at Week 4 (i.e., if all doses have $> -0.4$ point difference over placebo using the Week 4 dose response model estimates for change from baseline in DAS28(CRP)).
Interim 2	90 subjects complete Week 12	PAREXEL: ADAM datasets and demography table (see Table 5 )  GSK: efficacy displays (see Table 5 ) and PK if required	Unblinded PAREXEL programmers, GSK lead and QC statistician, DRC	Evaluate whether to stop the study based on: • Dose response relationship at Week 12 (i.e., if all doses have $> -1.0$ point difference over placebo using the Week 12 dose response model estimates for the change from baseline in DAS28(CRP)). • Dose response relationship and predictive probabilities (i.e., if at least one dose $\leq -1.0$ over placebo using the Week 12 dose response model estimates but the predictive probabilities of seeing a 25% difference at Week 24 in DAS28(CRP) remission is $<30\%$ ). Evaluate whether to drop a treatment arm based on: • An individual dose with $> -1.0$ point difference over placebo using the Week 12 dose response model estimates for change from

				baseline in DAS28(CRP).
Week 24	All subjects complete Week 24 visit	PAREXEL: Unblinded Week 24 displays.	PAREXEL lead and QC biostatisticians and programmers, GSK.	Unblinded primary/secondary analyses, safety and PK.
Final	All subjects complete the study (follow-up visit at Week 62)	PAREXEL: All unblinded displays, including exploratory endpoints, SDTM and ADAM datasets.	PAREXEL lead and QC biostatisticians and programmers, GSK.	Final reporting for Study 201755.

Unblinded interim analyses will be conducted when 90 subjects (i.e. on average 15 per arm) have completed 4 and 12 weeks of treatment. Efficacy analysis for the interim analyses will not be analysed by PAREXEL but by GSK. These interim analyses will be aligned with the unblinded safety review of the DRC where possible, see section [4.10.11](#).

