**Table 5 List of Outputs for Interim Analyses (IA)**

Endpoint	Output	IA1	IA2	Produced by
n/a	Summary of Demography Characteristics – Disease History	Y	Y	PAREXEL 
DAS28(CRP) change from baseline	Summary of the Change from Baseline in DAS28(CRP) at Each Visit	Y	Y	GSK
	Plot of Mean and 95% CI of Change from Baseline in DAS28(CRP) by Visit and Randomised Treatment Group (1 plot)	Y	Y	GSK
	Plot of Mean and 95% CI of Change from Baseline in DAS28(CRP) Across Doses at Weeks 4, 8 and 12 (3 plots)	Y	Y	GSK
	Mixed Model Repeated Measures Analysis (MMRM) of Change from Baseline in DAS28(CRP) Through Week 12	Y	Y	GSK
	Plot of Least Squares Means and 95% CI of Change from Baseline in DAS28(CRP) (from MMRM)	Y	Y	GSK
	Dose Response Modelling of Change from Baseline in DAS28(CRP) at Weeks 4, 8 and 12	Y	Y	GSK
	Plot of Dose Response Model at Weeks 4, 8 and 12	Y	Y	GSK
DAS28(CRP) remission	Posterior Probability of the Difference in the Change from Baseline over Placebo < -1.0 at Week 12 for Each Dose	Y	N	GSK
	Proportion of Subjects in DAS28(CRP) Remission at Week 24	N	Y	GSK
ACR response	Predictive Probability of the Difference Over Placebo in the Proportion of Subjects in DAS28(CRP) Remission at Week 24 being > 25%	N	Y	GSK
	Proportion of Subjects with an ACR20/50/70 Response at Each Visit	Y	Y	GSK

 Produced by the unblinded programming team.

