Markov-Chain-Monte-Carlo (MCMC) methods in SAS® will be used to derive the posterior distributions for each randomised treatment group and to also derive the distribution of the difference between each treatment group and the placebo group. From this difference distribution the posterior probability that the treatment difference between each active dose and placebo being  $> 1$  will be calculated.

Decision criteria for stopping the study after Interim Analysis 1 are specified in the DRC Statistical Guidance Document.

## DAS28 (CRP) remission rates at Week 24

The number and percentage of subjects achieving DAS28(CRP) remission ( $DAS28(CRP) < 2.6$ ) will be summarised for each randomised treatment group and visit. Fisher's exact test will be used to test for randomised treatment group differences at Week 24 in the proportion of subjects achieving remission for each GSK3196165 treatment group versus placebo.

## Predictive Probabilities at Week 24

The proportion of subjects with available DAS28(CRP) remission data at week 24 at the interim analysis will only be summarised using counts and proportions. This is because only a low number of subjects with week 24 data are expected at the week 12 interim analysis.

In addition, the predictive probability that the difference in DAS28(CRP) remission between each dose and placebo at the end of the study is  $> 15\%$  and  $> 25\%$ , given the results at the interim analysis and the prior information will be calculated using the procedure described below.

The following information will be available at the interim:

- $l_i$  = number of subjects that have reached week 24 in each randomised treatment group  $i$ ,  $i=0, \dots, 5$  ( $i=0$  being the placebo arm and  $i=1-5$  being the 5 treatment groups, with  $i=1$  being 22.5mg)
- $x_i$  = observed number of subjects in DAS28 remission at week 24 in each randomised treatment group  $i$ ,  $i=0, \dots, 5$  ( $i=0$  being the placebo arm and  $i=1-5$  being the 5 treatment groups, with  $i=1$  being 22.5mg)

Our prior Beta distribution on the remission rate in each randomised treatment group:  
 $\pi_i \sim \text{Beta}(\alpha_i^0, \beta_i^0)$

- Placebo:  $\alpha_0^0 = 9$ ,  $\beta_0^0 = 91$ , so the prior mean remission rate is 9%, and the 95th interval is (4%, 15%)
- Active group:  $\alpha_i^0 = 1$ ,  $\beta_i^0 = 1$ , equivalent to a uniform distribution (non informative). This will apply to all active groups ( $i=1$  to 5)

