The algorithm is as follows:

1. Compute the interim posterior distribution of the remission rate  $\pi_i$  in each randomised treatment group:

$$\pi_i \sim \text{Beta}(\alpha_i = \alpha_i^0 + x_i, \beta_i = \beta_i^0 + l_i - x_i)$$

2. For each of the 6 treatment groups, a sample of the number of subjects with DAS28 remission post-interim is generated from the following predictive distribution (Beta-Binomial):

$$y_i \sim \text{beta-Binomial}(\text{sample} = m_i - l_i, \alpha_i, \beta_i)$$

Where  $m_i - l_i$  is the number of subjects remaining post-interim,  $\alpha_i$  and  $\beta_i$  are the parameters of the interim posterior distribution of the remission rate as calculated in (1).

10,000 replicates will be used per treatment group.

3. For each replicate, compute the distribution of the remission rate in each treatment group:

$$\pi_j \sim \text{Beta}(\alpha_i + y_i, \beta_i + m_i - y_i)$$

and therefore generate a sample of 10,000 simulations.

For each treatment group, we will obtain a matrix with 10000x10000, each column corresponding to the predictive distribution of  $\pi_i$  for each replicate from (2).

4. Calculate the posterior predictive distribution of the difference  $\pi_i - \pi_0$ , for  $i = 1, \dots, 5$   
For each of the 5 differences, we obtain again a matrix with 10000x10000, each column corresponding to the predictive distribution of the difference for each replicate from (2).
5. The posterior predictive probability  $p_j = P(15\% < \pi_j - \pi_0 < 25\%)$ ,  $j=1, \dots, 5$ , is calculated empirically by counting how many times the rule is met in the sample of the difference for each replicate. The median is used over the 10,000 replicates.

For sensitivity analysis purposes, other prior distributions for the placebo arm may be assessed based on emerging data on this endpoint, including assuming a non-informative prior.

The predictive probabilities to have an improvement of 25 percentage points over placebo will be used for the decision making, i.e. potentially dropping treatment arms or stop the study for futility. Decision criteria are specified in the DRC Statistical Guidance Document.

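### The Week 24 predictive-probability algorithm for Interim 2 does not compute the probability the futility rule uses: step 5 takes a 15–25% window, and step 3 counts interim subjects again as failures

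*SAP*

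**What the plan says.** SAP 4.9.2.1, under Predictive Probabilities at Week 24, sets out a five-step algorithm.

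- Step 1 forms the interim posterior for each arm as "Beta}(\alpha_i = \alpha_i^0 + x_i, \beta_i = \beta_i^0 + l_i - x_i", where l_i subjects have reached Week 24 and x_i of them are in remission.
- Step 2 draws y_i, the future remitters, from a beta-binomial with those same parameters and sample size m_i − l_i, which "is the number of subjects remaining post-interim".
- Step 3 updates to "Beta}(\alpha_i + y_i, \beta_i + m_i - y_i".
- Step 5 defines the result as "p_j = P(15\% < \pi_j - \pi_0 < 25" per cent and takes the median over replicates.

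The same SAP describes the target quantity in four other places.

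- The lead-in to the algorithm names two separate one-sided thresholds to be exceeded, of 15 and 25 percentage points, for this quantity: "the predictive probability that the difference in DAS28(CRP) remission between each dose and placebo at the end of the study is".
- Table 5 lists the Interim 2 output as "Predictive Probability of the Difference Over Placebo in the Proportion of Subjects in DAS28(CRP) Remission at Week 24 being > 25" per cent.
- Table 4 has stopping evaluated, when at least one dose meets the Week 12 criterion, if "the predictive probabilities of seeing a 25% difference at Week 24 in DAS28(CRP) remission is" below 30%.
- The closing paragraph of the algorithm states: "The predictive probabilities to have an improvement of 25 percentage points over placebo will be used for the decision making". It names both dropping arms and stopping for futility.

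**The concern.** There are two separate faults.

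Step 5 measures a bounded interval where the rule needs an upper tail. The window probability is low for an inert dose and low again for a dose that clearly beats placebo by more than 25 points. A 30% floor applied to it would count strong efficacy as futility.

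Step 3 double-counts. All l_i interim subjects are already in α_i and β_i, so only the m_i − l_i new subjects should be added. As written, each interim subject, including those in remission, is entered again as a failure. The active prior is worth 2 subjects and the placebo prior 100, so the surplus pulls the active rate down far more than the placebo rate and biases the difference downward.

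At stake is one limb of the Interim 2 decision whether to stop the study. Stopping an effective programme or arm on a mis-specified number cannot be undone.

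**Working it through.** **Inputs.** Placebo prior Beta(9, 91), active prior Beta(1, 1), and the median over replicates are from SAP 4.9.2.1. m = 35 per arm is from SAP 4.13.1. The 30% limit is from SAP Table 4. The true active rates of 33% and 45% are from SAP 4.13.1 and Table 11. The SAP gives no l_i, so l = 1 to 12 per arm is assumed, with placebo at 0/l unless stated.

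**The plan's own figure.** Beta(9, 91) has mean 9/100 = 9% and 2.5% and 97.5% quantiles of 4.2% and 15.3%. The SAP's 9% (4%, 15%) is reproduced.

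**Step 3 algebra.** Step 1 gives α_i + β_i = α⁰ + β⁰ + l. Step 3 as written adds y + (m − y) = m, so the parameters sum to α⁰ + β⁰ + l + m. A correct update adds y + (m − l − y) = m − l, so they sum to α⁰ + β⁰ + m. The surplus is exactly l, all of it in the failure parameter.

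Example with l = 5 and m = 35: the active total is 2 + 5 + 35 = 42 instead of 37, and the placebo total is 140 instead of 135. With 12/35 active remitters the posterior mean is 13/42 = 0.310 instead of 13/37 = 0.351. With 3/35 placebo remitters it is 12/140 = 0.086 instead of 12/135 = 0.089. The difference drops from 0.262 to 0.224, which crosses the 25-point mark.

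**Full algorithm.** For each (l, x), every pair of future remitter counts was weighted by its beta-binomial probability, P(difference) was obtained by numerical integration, and the weighted median was taken.

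Largest value of step 5 as written, over all possible active outcomes:

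| l | 1 | 2 | 3 | 4 | 5 | 6 |
|---|---|---|---|---|---|---|
| maximum | 0.05 | 0.07 | 0.13 | 0.18 | 0.21 | 0.26 |

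For l up to 6, no result can reach 0.30. From l = 7 some moderate results pass (2/7 gives 0.31, 3/10 gives 0.37), while stronger ones fail:

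| active x/l | as written | both steps corrected |
|---|---|---|
| 3/6 | 0.10 | 0.97 |
| 4/8 | 0.14 | 0.98 |
| 5/10 | 0.16 | 0.98 |
| 6/12 | 0.21 | 0.98 |
| 3/12 | 0.32 | 0.23 |

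The last row shows that the error can also run the other way. One placebo remitter changes little: 4/8 against 1/8 gives 0.15 as written and 0.97 corrected; 5/10 against 1/10 gives 0.21 and 0.97.

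**Step 3 error alone** (step 5 corrected to > 25%): 2/7 falls from 0.42 to 0.19, 3/9 from 0.61 to 0.27, 3/10 from 0.45 to 0.15, and 4/12 from 0.59 to 0.18. Each crosses 30%.

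**Chance of a false reading below 30% for one dose.** This is the binomial probability of the outcomes where the corrected value is at least 30% and the as-written value is below it. For l = 6 those are x ≥ 2; at a 33% rate, 1 − 0.67⁶ − 6(0.33)(0.67⁵) = 0.64. For l = 10 they are x ≥ 5, with probability 0.21.

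| true active rate | l = 6 | l = 8 | l = 10 | l = 12 |
|---|---|---|---|---|
| 33% | 0.64 | 0.25 | 0.21 | 0.17 |
| 45% | 0.84 | 0.52 | 0.50 | 0.47 |

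**The case against.** The intended target is clear elsewhere in the SAP, and step 5 may be shorthand for the two thresholds of 15% and 25%. A programmer producing the output titled in Table 5 would have to count differences above 25%. Table 4 says evaluate, not stop; SAP 3.1.4 has the DRC's recommendation ratified by a steering committee; and the formal criteria are in a guidance document not seen here. All of that stands, and it limits what can be said about the decision actually taken. It does not make step 5 correct, and it does not touch step 3, an indexing slip that the surrounding text would not reveal.

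Step 3 alone often leaves the reading on the same side of 30%: 2/5 goes from 0.84 to 0.68, 3/6 from 0.97 to 0.90, 5/10 from 0.98 to 0.81. Its surplus equals l, so it shrinks when few subjects have reached Week 24. That is fair; step 5 is the dominant error. But 2/7 shows that step 3 can change the reading at a low l.

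The per-dose chances are not study-stop chances. Table 4 does not say how many doses must fall below 30%. If all five must, with every true rate at 33%, the as-written chance is about 0.2 at l = 8, 0.04 at l = 10 and 0.006 at l = 12. The corrected steps give about 0.011 at l = 12, so the literal version is no worse there. For l up to 6 it fails every dose with certainty.

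The reversal at 3/12 depends on the median; with the mean over replicates the values are 0.30 and 0.33. The corrected steps also still summarise a posterior probability about true rates, not the probability of an observed difference in proportions. That is a separate matter of definition.

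**Conclusion.** The concern holds and must be fixed. Step 5 contradicts four other statements in the SAP, and step 3 adds exactly l_i failures to every arm by the SAP's own definitions. Coded literally, the output does not rank doses by effect. It cannot reach 30% for l of 1 to 6, and beyond that it gives strong doses values of 0.14 to 0.21 where about 0.98 is right. These sizes assume m = 35, l of 1 to 12, placebo remitters as stated and the median summary; the two errors themselves need no assumption. No conclusion is drawn about the executed program or the DRC criteria, which the supplied documents do not show.

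**What to change.** In SAP 4.9.2.1, change step 3 to π_i ~ Beta(α_i + y_i, β_i + m_i − l_i − y_i), with one index throughout. Change step 5 to p_j = P(π_j − π_0 > 25%) for the decision, and report P(π_j − π_0 > 15%) separately. Keep the pre-specified median over replicates. Before Interim 2, confirm that the DRC Statistical Guidance Document and the program use the same formulas.

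As a wording point only, reconcile the sign of the Week 12 posterior criterion: the text has a difference greater than 1, Table 5 has less than −1.0. It is an Interim 1 output and does not enter the Interim 2 rule.

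The cost is two formula edits and one check of the guidance document and program. It needs no additional subjects and no protocol amendment.

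### Step 5 of the Week 24 futility calculation reports a median over replicates, which is not the predictive probability compared with 30% and is too low near that line

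*SAP*

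**What the plan says.** SAP Section 4.9.2.1, under Predictive Probabilities at Week 24, sets the target: the predictive probability, given the interim results and the priors, that the end-of-study remission difference from placebo exceeds 15 or 25 points. The algorithm has five steps. Step 2 draws future remitters from a beta-binomial distribution ("10,000 replicates will be used per treatment group"). Steps 3 and 4 form the posterior of the rate difference for each replicate. In step 5 the probability "is calculated empirically by counting how many times the rule is met in the sample of the difference for each replicate", and then "The median is used over the 10,000 replicates".

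The same section says which figure matters: "The predictive probabilities to have an improvement of 25 percentage points over placebo will be used for the decision making". Table 4 (Interim 2) gives, as one ground for considering a study stop, that at least one dose passes the Week 12 criterion but "the predictive probabilities of seeing a 25% difference at Week 24 in DAS28(CRP) remission" is below 30%. The SAP gives no reason for the median and no recalibration of the 30% for it. Decision details are left to the DRC Statistical Guidance Document, which is not among the documents.

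**The concern.** Each replicate of the future data yields one posterior probability that the difference exceeds 25 points. With few Week 24 subjects at the interim, most of the information is still to come, so these probabilities are widely spread and skewed. When the typical replicate looks poor but a sizeable minority look good, the median sits well below the average. That is the situation near 30%. The figure shown to the DRC would then understate a dose's chance of success just where it is compared with the futility line, and nothing in the SAP warns that the line and the statistic do not match.

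**Working it through.** **Inputs.**
- Priors from SAP Section 4.9.2.1: placebo Beta(9, 91); each active dose Beta(1, 1), which the SAP calls "equivalent to a uniform distribution (non informative".
- Final size m = 35 per arm (SAP Section 4.13.1).
- Decision rule: difference above 25 points.
- Week 24 subjects per arm at the interim, l: not given. The SAP says only that few are expected. The assumed range is 3 to 15, where 15 is the average number per arm with Week 12 data (90/6).

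**Reproducing the plan's own figure.** Beta(9, 91) has mean 9/100 = 9% and equal-tailed 95% interval 4.2% to 15.3%; the SAP prints 9% and 4% to 15%. The SAP gives no worked predictive probability.

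**Formulas.** Write x of l for active remitters and x0 of l for placebo.
- Interim posteriors: Beta(1 + x, 1 + l − x) and Beta(9 + x0, 91 + l − x0).
- Future remitters y and y0: beta-binomial on 35 − l subjects with those parameters.
- Per-replicate probability: g(y, y0) = P(π_i − π_0 > 0.25) under Beta(1 + x + y, 36 − x − y) and Beta(9 + x0 + y0, 126 − x0 − y0). This is step 3 with the correct remaining count.
- By iterated expectation, the average of g over (y, y0) equals P(π_i − π_0 > 0.25) given the interim data. No such identity holds for the median of g.

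**Hand check, 1/5 v 0/5.** The active posterior is Beta(2, 5), whose upper tail beyond t is (1 − t)^5 (1 + 5t). The placebo posterior is Beta(9, 96), mean 9/105 = 0.0857. At t = 0.25 + 0.0857 = 0.3357 the tail is 0.6643^5 × 2.6785 = 0.1294 × 2.6785 = 0.347. Integrating over the placebo posterior gives 0.349, the mean below.

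**Exact enumeration of all (y, y0).** The last column is the share of replicates whose observed final difference exceeds 25 points.

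| Active v placebo remitters | Mean of g | Median of g | Share, observed difference |
|---|---|---|---|
| 1/5 v 0/5 | 0.349 | 0.183 | 0.364 |
| 2/8 v 1/8 | 0.358 | 0.233 | 0.326 |
| 3/12 v 1/12 | 0.311 | 0.207 | 0.286 |
| 4/15 v 1/15 | 0.333 | 0.260 | 0.324 |

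For 2/8 v 0/8 the mean is 0.380 and the median 0.261. In all five settings the mean is above 30% and the median below it, and the mean agrees with the direct interim posterior probability. Monte Carlo with 10,000 replicates agreed with the enumeration in two further settings (3/10 v 1/10: 0.449 and 0.410, exact 0.453 and 0.416; 2/5 v 0/5: 0.673 and 0.843, exact 0.675 and 0.844).

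**Where the line really sits.** Interpolating over the remitter count, a median of 0.30 corresponds to a mean of about 0.35 (l = 15) to 0.42 (l = 3).

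**Sensitivity.** With m = 50, 1/5 v 0/5 gives 0.349 v 0.146. With a flat placebo prior, 3/10 v 1/10 gives 0.308 v 0.181. With step 3 as printed, a median of 0.30 still corresponds to a mean of 0.35 to 0.42.

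**The case against.** **The event is not settled.** The target text refers to the difference at the end of the study, and Table 4 to seeing a 25% difference at Week 24. Either can mean the observed final difference. On that reading the right summary is the share of replicates meeting the rule, and for 3/12 v 1/12 it is 0.286, below 30% like the median. The mean also equals the interim posterior probability, so for the true-rate event it makes the simulation of future data unnecessary. This stands, and the fix must start by naming the event. It does not rescue the median: for 1/5, 2/8 v 1/8 and 4/15 the observed-difference share is also above 30% while the median is below.

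**The size depends on another repair.** Step 5 prints a window, a difference between 15 and 25 points. Under that window, with step 3 corrected, the shift is small and can go upward (3/12 v 1/12: mean 0.309, median 0.348). This stands too, but the window is not the decision quantity in Table 4 or in the closing text of the section.

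**A reader might infer that the study would be stopped wrongly.** The documents do not support that. Table 4 lists a criterion for evaluation, covers five doses without saying how their figures combine, and refers to guidance not supplied; SAP Section 3.1.4 has a steering committee ratify a stop. For illustration, take five Week 24 subjects per arm and no placebo remitters. The median puts a dose below 30% at 0 or 1 remitters (0.001, 0.183), the mean only at 0 (0.088). At the 33% design rate these chances are 0.67^5 + 5 × 0.33 × 0.67^4 = 0.135 + 0.3325 = 0.47, against 0.135. If all five doses had to fall below, with arms treated as independent, the chances are 0.4675^5 = 0.022 and 0.135^5, under 0.0001. The single-dose figure is often affected; a study stop would be rare on that reading.

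**A reader might also say that the median is not a probability, or that it drifts toward either extreme around 30%.** Neither holds. It lies between 0 and 1, and near 30% it moves only toward 0. The drift toward 1 appears when the mean is above about 0.5 (2/5 v 0/5: 0.675 against 0.844).

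**Conclusion.** The median in step 5 is not the predictive probability that the section defines and Table 4 compares with 30%. For the more-than-25-points rule, the nominal 30% line behaves like a line at about 35% to 42%, so a dose can be shown below 30% when its predictive probability is above it. The figure given to the DRC is biased toward futility. This rests on 35 per arm at the end, the SAP's priors, step 3 corrected and assumed Week 24 counts. The downward shift near 30% held across the counts from 3 to 15 that were tried.

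The conclusion stops at the dose-level figure. Whether the 30% was calibrated to the median elsewhere cannot be seen; nothing in the SAP says so.

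**What to change.** State the event in step 5 first, then choose the matching summary.
- True rate difference above 25 points: replace the median with the mean over the 10,000 replicates.
- Observed end-of-study difference above 25 points: report the share of replicates meeting the rule (0.364 for 1/5 v 0/5).

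Make the DRC Statistical Guidance Document match, including how the five dose-level figures are combined. Make this change together with two separate corrections in the same algorithm. Step 3 should use the number remaining after the interim, m_i − l_i − y_i; as printed, m_i − y_i counts the l_i observed subjects again as non-remitters. Step 5 should use the more-than-25-points rule in place of the 15 to 25 window. The median change costs one sentence in the SAP and one line of code; no data collection changes.
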